- Must have biopsy-proven desmoid tumor (or aggressive fibromatosis). For patients with recurrent disease, a biopsy is not required at the time of recurrence.
- Patients known to have germ-line APC mutations or clinical manifestations of FAP/Gardner's syndrome can be included.
- Patients must have surgery planned to remove the desmoid tumor and either:
 - a) The desmoid tumor has already recurred after a prior surgery or
 - b) The newly diagnosed and/or previously unresected disease is judged to be at high risk for recurrence due to its size (> 5 cm) or location at an anatomic site making it unlikely to be resected with negative margins (e.g., adjacent to neurovascular structures)
- There must be a commitment by the surgical team to resect the primary tumor within 3 days following the 4 weeks of sirolimus unless the clinical situation at the time of resection suggests that these interventions are not in the patient's best interest.
- Concomitant medication restrictions:
 - a) Patients may have received prior chemotherapy (excluding prior mTOR inhibitors).
 - b) Use of steroids for non-tumor indications (e.g., asthma or severe allergic reaction) is permitted.
- Patients must have a Karnofsky performance status \geq 50 for patients > 16 years of age or Lansky performance status \geq 50 for patients ≤ 16 years of age.
- Patients must have a life expectancy \geq 8 weeks.
- Patients must have recovered from the acute toxic effects of all prior chemotherapy, immunotherapy, or radiotherapy prior to entering this study.
 - a) Myelosuppressive chemotherapy: Must not have received within 2 weeks of entry onto this study (4 weeks if prior nitrosourea).

- b) Biologic (anti-neoplastic agent): At least 7 days since the completion of therapy with a biological agent.
- c) Stem Cell Transplant (SCT): No evidence of active graft vs. host disease. For allogeneic SCT, \geq 6 months must have elapsed.
- Patients must be able to consume oral medication in the form of tablets or solution.
- Patients must have normal laboratory values as defined below:
 - Creatinine clearance or radioisotope GFR \geq 70ml/min/1.73m² or
 - - A serum creatinine based on age/gender as follows:

Age	Maximum Serum Creatinine (mg/dL)	
	Male	Female
1 month to < 6 months	0.4	0.4
6 months to < 1 year	0.5	0.5
1 to < 2 years	0.6	0.6
2 to < 6 years	0.8	0.8
6 to < 10 years	1	1
10 to < 13 years	1.2	1.2
13 to < 16 years	1.5	1.4
\geq 16 years	1.7	1.4

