- Anticipated or unanticipated surgical delay beyond 3 days should be discussed with the study PI to determine if a patient should be removed from protocol therapy.

Note about Postoperative Chemotherapy

- *The pilot study is complete following tumor resection. If the treating physician chooses to continue sirolimus following resection, for example, based on symptomatic improvement, it will be independent of this clinical trial.*

DRUG ADMINISTRATION GUIDELINES:

- **Sirolimus**
 - Prior to beginning and each week, the following laboratory criteria must be met before beginning or continuing Sirolimus:
 - ANC $\geq 0.75 \times 10^9/L$
 - Platelets $\geq 75 \times 10^9/L$
 - Serum creatinine $\leq 2 \times$ baseline or GFR $\geq 70 \text{ mL/min}/1.73 \text{ m}^2$
 - Total bilirubin 0 – 21 $\mu\text{mol/L}$ (0 -1.24 mg/dL)
 - Sirolimus is to be administered daily by mouth.
 - The drug may be given without regard to food, but should be consistently administered the same way (with or without food).
 - The oral solution may be diluted in 2 ounces of water or orange juice immediately prior to administration. The glass should be rinsed with an additional 4 ounces of the same fluid and administered to the patient.
 - Dose adjustments will not be made based on trough levels.

DRUG MODIFICATIONS FOR TOXICITY

If the patient suffers any Grade 3 or 4 toxicity that the treating physician feels may delay surgery, the patient will come off study.

Dose Modifications for Sirolimus

Toxicity	Criteria/Grade	Action												
Myelosuppression	ANC < 0.75 x 10 ⁹ /L Plts < 75 x 10 ⁹ /L	Withhold sirolimus, and repeat within 3-4 days until neutropenia or thrombocytopenia are resolved. If no previous delay, resume at full dose. If previous delay, reduce dose by 25%.												
Mucositis, Severe Abdominal Pain, Diarrhea	Grade 4 mucositis or repeated Grade 3 mucositis	Delay until resolved and decrease subsequent sirolimus dose by 25%.												
Renal Toxicity	Serum creatinine > 2 x baseline or GFR < 70 mL/min/1.73 m ²	Delay for one week and decrease subsequent sirolimus dose by 25%. If renal function does not improve, discontinue sirolimus.												

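### The renal criterion for continuing sirolimus and the renal toxicity trigger are not complements: where a GFR is available, a patient breaching exactly one limit satisfies both, and no text says which governs

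*Combined protocol and SAP*

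**What the plan says.** Three places in the combined protocol and SAP set renal limits.

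- **Drug Administration Guidelines.** The list opens: "Prior to beginning and each week, the following laboratory criteria must be met before beginning or continuing Sirolimus". Its renal entry is met by a serum creatinine of at most 2 x baseline, or by a GFR of at least 70 mL/min/1.73 m².
- **Dose Modifications for Sirolimus, Renal Toxicity row.** The criterion is "Serum creatinine > 2 x baseline or GFR < 70 mL/min/1.73 m ²". The action is "Delay for one week and decrease subsequent sirolimus dose by 25" per cent, with discontinuation if renal function does not improve.
- **Eligibility, Inclusion criteria.** Entry can rest on "Creatinine clearance or radioisotope GFR" of at least 70 or, as an alternative, on "A serum creatinine based on age/gender as follows", followed by a table of maxima. The protocol states that these maxima were derived from the Schwartz formula for estimating GFR.

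The Required Observations table schedules creatinine weekly during the course, and a weekly physical examination that includes height. It has no GFR row. Under Criteria For Removal From Protocol Therapy, a patient who missed more than 25% of sirolimus doses is removed.

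**The concern.** A rule for when drug may be given and a rule for when it must be held should divide patients cleanly. The opposite of meeting at least one of two limits is breaching both. The toxicity row instead applies when at least one is breached, so the two rules overlap.

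The neutrophil and platelet limits in the same sections do divide cleanly: at least 0.75 against below 0.75, and at least 75 against below 75 (x 10⁹/L). The renal pair is therefore out of step with its neighbours.

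What is at stake is consistency. Two sites could handle the same renal results differently, one holding for a week and then reducing, the other dosing on. The primary endpoint is tumor immunohistochemistry after 4 weeks of sirolimus in 15 patients, so each patient is 1/15 = 6.7% of the treated group. Uneven holds and reductions would alter the exposure behind that comparison.

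**Working it through.** The plan gives no figure to reproduce here; the check is one of logic.

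**Step 1. The four combinations.** Let A be creatinine at most 2 x baseline, and B be GFR at least 70. The criterion for continuing is (A or B). The toxicity trigger is (not A or not B).

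| Creatinine ≤ 2 x baseline (A) | GFR ≥ 70 (B) | Renal criterion for continuing met | Toxicity row triggered | Both |
|---|---|---|---|---|
| yes | yes | yes | no | no |
| yes | no | yes | yes | **yes** |
| no | yes | yes | yes | **yes** |
| no | no | no | yes | no |

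Two of the four combinations satisfy both rules. If one rule were made the exact complement of the other, the count would fall to 0 of 4. That is a logical check only and does not favour either wording.

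**Step 2. When only creatinine is known.** The rules reduce to at most 2 x baseline against more than 2 x baseline, which are complements. The overlap therefore needs a GFR as well as a creatinine.

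**Step 3. Day 1.** Take a patient who entered through the creatinine table and whose GFR is below 70. Creatinine is 1 x baseline, so the renal criterion for beginning is met. The GFR part of the toxicity row refers to an absolute value and not to a change, so the trigger is met too.

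**Step 4. Width of the overlap, under an assumption.** Suppose GFR is inversely proportional to creatinine. The documents do not say this, and they give no baseline GFR values. GFR then falls below 70 once the creatinine ratio to baseline exceeds (baseline GFR)/70.

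| Assumed baseline GFR | Ratio at which GFR reaches 70 | Ratios meeting both rules |
|---|---|---|
| 70 | 70/70 = 1.00 | just above 1.00 to 2.0 |
| 80 | 80/70 = 1.14 | 1.14 to 2.0 |
| 100 | 100/70 = 1.43 | 1.43 to 2.0 |
| 120 | 120/70 = 1.71 | 1.71 to 2.0 |
| 140 | 140/70 = 2.00 | none |
| 150 | 150/70 = 2.14 | 2.0 to 2.14 (creatinine limit breached, GFR limit met) |

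**Step 5. Doses.** The course is the loading dose plus days 2 to 28: 1 + 27 = 28 doses. A one-week hold is 7/28 = 25.0%, at the removal limit but not above it. One further missed dose gives 8/28 = 28.6%, above the limit if held doses count as missed. The protocol does not say whether they do.

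**The case against.** The strongest reply is that the two texts can be obeyed together. The laboratory list states what must hold before dosing; it is a necessary condition alongside the neutrophil, platelet and bilirubin limits, and not an order to dose. Only the toxicity row prescribes an action, so a patient who meets the list and triggers the row is simply held. This stands to the extent that nobody is literally told to continue and to stop, although a reader might infer that. It does not settle the matter. The protocol nowhere gives the table precedence, and if the table always prevailed, the alternative in the renal criterion would permit nothing that the table did not then withdraw.

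The second reply is that the alternative means whichever measure is available, and that GFR is not scheduled. With creatinine alone there is no overlap, as step 2 shows. This is a fair reading and it limits the point, but the text does not state it. A site could estimate GFR from the creatinine and height already collected weekly, using the kind of formula that the protocol cites for its own creatinine maxima. One site may do so and another not.

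Third, the toxicity table under Agent Information lists increased creatinine as common (21-100%), from which a reader might infer that the conflict is frequent. That entry gives no grade or size of rise, and nothing on how often GFR would be below 70 with creatinine still within 2 x baseline. Likewise, the entry maxima were built as a surrogate for GFR. Discordance at entry is possible for an individual, but the documents do not show that it is usual.

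**Conclusion.** The two renal rules are inconsistent as written and need reconciling. The inconsistency covers 2 of 4 creatinine/GFR combinations, in both directions, and includes a possible day-1 case. It arises only where both measures are available, which the schedule neither requires nor rules out. The bands in step 4 depend on the inverse-proportionality assumption and on assumed baseline values; they show where an overlap could lie, not how many patients would fall in it.

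A reader might also infer that this ambiguity decides who is removed from protocol therapy. The documents do not support that: a one-week hold is exactly 25% and the limit is more than 25%. Removal would need a further missed dose and a rule that held doses count as missed.

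This is a defect in the wording of a safety rule, with a possible effect on how uniform exposure is before the primary endpoint. It does not invalidate the design or the planned analysis. Nothing here says which renal limit is clinically right.

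**What to change.** Reconcile the eligibility, continuation and toxicity passages so that every creatinine/GFR combination leads to one action. State which measure applies when only creatinine is available and when both are, and whether an estimated GFR counts. Say how the toxicity row applies to a GFR already below 70 before the first dose. State whether doses held under the protocol count towards the missed-dose limit. The clinical team should decide which limit governs.

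The cost is a wording amendment, with submission to the local IRBs of a multi-site study. Sample size and analysis are unaffected.

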H and E staining will be used to verify that the arrayed tissue/slides contain desmoid-type fibromatosis. To assess mTOR pathway activation, immunohistochemical staining will be conducted for the following proteins and phosphoproteins: p-p70S6K, p-4E-BP1, both of which represent targets of mTOR; and p-AKT as this pathway could be activated as a drug resistance mechanism (see Figure 1). Staining will be performed on the (a) post-treatment specimens, (b) paired, pre-treatment, archived specimens (if available), and (c) archived non-chemotherapy-treated specimens from the UCLA tumor bank (approximately 50 are available). All samples will be anonymized using an alpha-numeric code, with the key maintained in a HIPAA-compliant, secure database or locked file on the UCLA Server.

Routine histology protocols (including positive and negative controls) will be used. Quantitative analysis will be accomplished utilizing an Immuno-Reactive Score (IRS) as previously described (Noske et al., 2008; Chen et al., 2009; Lin et al., 2006). Specifically, the percentage of positive cells will be scored as: 0 (0%); 1 (<10%); 2 (11-50%); 3 (51-80%); 4(>80%). The staining intensity will be scored as: 0 (negative), 1 (weak), 2 (moderate), and 3 (strong). To derive the IRS, the percentage of positive cells and staining intensity will be multiplied together, resulting in a value from 0 to 12. IRS values 0 to 3 will be considered negative and values of 4 to 12 will be considered positive. Of note, samples will be scored by an experienced pathologist, blinded to whether the samples represent pre- or post-treatment or archived non-chemotherapy treated specimens.

Pain Assessment

Validated pain assessment measures, using the numeric and Wong-Baker FACES scales, will be collected at specific study time points. Patients ≥ 3 and < 10 years of age will use the Wong-Baker FACES scale and patients who are ≥ 10 years of age will use the numeric scale. A positive response will be associated with an improvement of $\geq 50\%$ from baseline after 4 weeks. A negative response will be associated with any worsening from baseline after 4 weeks. A stable response will be any other result.

Radiographic Assessment

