- A completed MedWatch form will be utilized for collecting adverse event information. Complete in the timeframe specified in guidelines above and fax to [contact] to the attention of [name]. In addition each site must report adverse events per their local IRB policy.

All delinquent reporting to the MMC/MCCP coordinating center must include documentation of reason for delinquency and may require implementation of an action plan.

Records, Reporting, and Study Monitoring –

Data Collection Forms:

Forms should be completed at specified time points and sent to:

[name]
Coordinator of Clinical Research
Maine Children's Cancer Program
[name]
[name]
[contact]
[contact]
Email- [contact]

Monitoring of Study Data:

As the coordinating center MMC/MCCP will monitor and review all data for accuracy and completeness, and will collect data quarterly. Queries will be generated to clarify unclear or missing data. Records of this review will be maintained at MMC/MCCP. Eligibility, deviations, adverse events and essential data elements will routinely be verified. As the coordinating center MMC/MCCP will obtain a copy of each local sites IRB approval and IRB approved informed consent documents and all subsequent IRB reportable changes. On an annual basis a random review of 20% of the data not previously reviewed will be performed.

Unidentified patient SAE data will be shared w/ Pfizer.

STATISTICAL ANALYSIS

Primary Objective

The primary scientific endpoint for patients enrolled on this pilot study is determine whether mTOR pathway activation decreases in patients with surgically-resectable desmoid tumor that is removed following pre-operative treatment with sirolimus. We anticipate finding that 4 weeks of sirolimus will result in decreased mTOR pathway activation, assessed using immunohistochemical (IHC) studies outlined above. IHC results after 4 weeks of sirolimus, scored on a scale of 0-12, from patients enrolled on the study will be compared with archived tumor samples from untreated patients using a two-sample t-test. The sample size of n=15 trial patients and n=50 historical controls will provide 80% power to detect a true difference in means of 2.6 points on the 12-point scale. While the t-test is fairly robust, if the data are highly non-normally distributed a nonparametric, rank-sum test will be applied instead. In addition, responses will be dichotomized as described above (negative <3, positive >4) and the

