
proportion positive compared between the two groups using Fisher's exact test. Finally, pre- and post-treatment values within patients enrolled on the trial will be compared using paired t or Wilcoxon, signed-rank tests.

Secondary Objectives

These scientific endpoints will be mostly exploratory, given the small numbers of patients enrolling in this pilot study. Nonetheless, we anticipate finding that 4 weeks of sirolimus will result in decreased tumor-associated pain. Pain assessments will be made using validated age-based pain assessment scales and compared pre- and post-treatment using a paired t test. Descriptively, the number of patients showing >50% improvement in their pain score, worsening pain, or between 0 and 50% improvement will be tabulated. Having decreased pain in approximately 60% of patients without substantial toxicity will be viewed as a success.

Patients will also be followed for recurrence post-surgery. As a benchmark, in a similar cohort of patients treated on the Pediatric Oncology Group 9650 study with vinblastine and methotrexate, the progression-free survival rate at 1 year was 58%. Vinblastine and methotrexate, which most would agree represents the current standard of care for desmoid tumor that is not amenable to surgery or radiation, is associated with significant toxicity: 18 of 27 (66%) patients on that trial experienced NCI grade 3 or 4 toxicity. Having histochemical evidence for decreased mTOR pathway activation with less toxicity will be viewed as a success, and lead the investigators to explore ways to test sirolimus in a randomized, phase II study in which the drug is used for patients with unresected disease and for patients in which the drug is continued following surgical resection of disease.

An independent statistician has been recruited from Center for Outcomes Research and Evaluation (CORE) at Maine Medical Center Research Institute. [name], assisted in the original presentation of this project. There will be no interim analysis performed; analysis will be performed at study completion. If [name] is not available, [name]. Senior Biostatistician at CORE, will be the lead statistician for this project. [name] will be assuming the analysis or consulting on this project as this is her area of expertise and her background is in translational research.

Early Stopping Rules

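### The analysis section prints IRS cut-offs of <3 and >4, which contradict the 0-3 / 4-12 definition and leave scores of 3 and 4 without a class in the Fisher comparison

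*Combined protocol and SAP*

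**What the plan says.** Histological Assessment builds the Immuno-Reactive Score (IRS) from a percentage-of-positive-cells score of 0 to 4 and an intensity score of 0 to 3: "the percentage of positive cells and staining intensity will be multiplied together, resulting in a value from 0 to 12". It then fixes the cut: "IRS values 0 to 3 will be considered negative and values of 4 to 12 will be considered positive".

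Statistical Analysis, Primary Objective, makes a two-sample t-test on the 0-12 score the main comparison, with a rank-sum test if the data are far from normal. As an additional comparison, "responses will be dichotomized as described above (negative <3, positive >4", with the "proportion positive compared between the two groups using Fisher's exact test". The two groups are the trial patients (n=15) and the archived untreated specimens (n=50).

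**The concern.** The analysis sentence claims to restate an earlier rule but states another. Histological Assessment is the only place above it that defines a cut. Against that definition, the printed thresholds take the score 3 out of the negative class and the score 4 out of the positive class, and put neither anywhere else.

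An analyst who programs the printed thresholds must either leave out specimens scoring 3 or 4 or place them by a rule that is not in the plan. With 15 trial specimens, a few such cases can change the proportions materially. If the choice is made after the scores are known, it is a choice made with the result in view.

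**Working it through.** **Inputs.** From Histological Assessment: percentage score 0, 1, 2, 3, 4; intensity score 0, 1, 2, 3; IRS is their product; negative 0-3, positive 4-12. From Statistical Analysis, Primary Objective: negative <3, positive >4; 15 against 50 specimens; Fisher's exact test on the proportion positive.

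**The plan's own figure.** No power or effect size is given for the Fisher comparison. The only design figure in the section belongs to the t-test: 80% power for a 2.6-point gap in mean score, with 15 against 50 specimens. It does not use the cut-off. It cannot be reproduced independently, because no SD, alpha or sidedness is stated. At an assumed two-sided alpha of 0.05 it implies SD = 2.6 / [(1.960 + 0.842) × √(1/15 + 1/50)] ≈ 3.15 by the normal approximation, or about 3.10 with the t distribution. Nothing below depends on it.

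**Step 1: which scores can occur.** The 5 × 4 = 20 combinations give the products 0, 1, 2, 3, 4, 6, 8, 9 and 12. Eight combinations give 0 and 12 give a non-zero product. The score 3 arises from 1×3 and 3×1, and the score 4 from 2×2 and 4×1. Together these are 4 of the 12 non-zero combinations. That is a count of combinations, not an expected share of specimens.

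**Step 2: class under each rule.**

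| IRS | Histological Assessment | Statistical Analysis, as printed |
|---|---|---|
| 0, 1, 2 | negative | negative |
| 3 | negative | none |
| 4 | positive | none |
| 6, 8, 9, 12 | positive | positive |

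**Step 3: can the difference matter?** The counts below are assumed. Each set gives the number of specimens scoring <3 / 3 / 4 / >4, trial against archived. Tests are two-sided.

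- Example A: 3/6/2/4 against 8/5/7/30
- Example B: 8/1/3/3 against 12/7/5/26
- Example C: 6/3/2/4 against 8/4/8/30

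| Example | Rule | Positive, trial | Positive, archived | Fisher p |
|---|---|---|---|---|
| A | 0-3 / 4-12 | 6/15 (40%) | 37/50 (74%) | 0.027 |
| A | 3 and 4 dropped | 4/7 (57%) | 30/38 (79%) | 0.34 |
| A | only >4 positive, full n | 4/15 (27%) | 30/50 (60%) | 0.038 |
| B | 0-3 / 4-12 | 6/15 (40%) | 31/50 (62%) | 0.15 |
| B | 3 and 4 dropped | 3/11 (27%) | 26/38 (68%) | 0.033 |
| B | only >4 positive, full n | 3/15 (20%) | 26/50 (52%) | 0.039 |
| C | 0-3 / 4-12 | 6/15 (40%) | 38/50 (76%) | 0.013 |
| C | 3 and 4 dropped | 4/10 (40%) | 30/38 (79%) | 0.045 |

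Dropping 3 and 4 weakens the comparison in A, strengthens it in B, and leaves p on the same side of 0.05 in C.

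**Step 4: range over assumed distributions.** Four base shapes on the attainable scores (weighted by number of combinations, flat, mid-peaked, bimodal) were exponentially tilted to archived means of 4, 5, 6, 7 and 8, with the trial mean 2.6 points lower. That gives 20 scenarios, each with 5,000 simulated trials of 15 against 50.

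- Share of a group scoring 3 or 4: 4% to 49%.
- Change in the expected gap in proportion positive (archived minus trial) when 3 and 4 are dropped: about -1 to +20 percentage points.
- Trials in which p crosses 0.05: 8% to 26%. From non-significant to significant: 3% to 19%. From significant to non-significant: 3% to 14%. Every scenario has crossings both ways.
- Fisher power: 0.35 to 0.85 under the definition, 0.31 to 0.88 with 3 and 4 dropped.

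**The case against.** The strongest reply is that the sentence corrects itself. It refers the reader back to the definition, and a dichotomy needs two classes that cover everything, so a careful analyst would use 0-3 / 4-12. That is probably right about intent. It does not make the printed thresholds correct, and it leaves one sentence carrying two rules.

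A second reply is that the equality bars were lost, either in drafting or when the PDF was read. There is support for this. Pain improvement is at least 50% in Pain Assessment but more than 50% in the analysis section, and the lower age limit for the FACES scale is inclusive in the body but strict in Appendix 1. The analysis section also contains no inclusive inequality sign at all. On the other side, such signs survive in Eligibility, in Drug Administration Guidelines and in Pain Assessment. A lost bar cannot be excluded from the text alone. If the source file prints ≤3 and ≥4, the point closes, because on whole-number scores that is the definition.

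A third reply is that the illustrations rest on invented counts, that no passage tells the analyst to discard specimens, and that the plan states no alpha for this test. All of that stands. Example C does not cross 0.05, and in example A keeping all specimens with only >4 positive gives p=0.038, on the same side as 0.027. The figures show that the choice can matter in either direction. They do not estimate an effect in this trial.

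Finally, the Fisher test is an additional analysis in a 15-patient pilot. That limits the consequence but does not remove the contradiction.

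**Conclusion.** The concern holds. The two sections state different cut-offs, and the printed one leaves two attainable scores, on either side of the intended cut, without a class. The contradiction itself needs no assumption beyond taking the supplied text as printed. Its effect on the Fisher result cannot be fixed in size or direction from the documents. Under assumed distributions with the planned 2.6-point difference, and with scores of 3 and 4 dropped, p crossed an assumed 0.05 level in 8% to 26% of simulated trials, in both directions.

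The reach is narrow. The comparison of mean or ranked scores, the within-patient tests, the sample size and the 80% power statement are unaffected. It should still be corrected before the scores are analysed, because it concerns a planned comparison under the primary objective.

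**What to change.** In Statistical Analysis, Primary Objective, replace the parenthesis with: negative 0-3, positive 4-12. Every specimen then has the class given in Histological Assessment, and all nine attainable scores are covered.

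This adopts the protocol's own definition. It changes no sample size, power statement or other test, and costs one corrected parenthesis.
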